***Observe quality and performance indicators among usual oncology care in similar patient-caregiver population to compare with cases.*** From non-treatment sites, identify, recruit, consent, and enroll persons with lung cancer (newly diagnosed or recent recurrence of disease) and their caregivers into the evaluation study. Recruitment will continue until 25 patients and 25 caregivers are enrolled (Control Dyads). Electronic health records for patients (appointment, clinical, and patient-reported data such as the M.D. Anderson Symptom Inventory that is standard of care) and study questionnaires will be used to evaluate quality and performance indicators however, questionnaires will be fielded at the post-period only. Non-treatment sites will not provide FCA as standard of care and function as control sites. These sites will include Geisinger Wyoming Valley in Wilkes-Barre, PA (“GWV”), and Geisinger Community Medical Center in Scranton, PA (“GCMC”). A case-matched controlled design will be used to evaluate differences in quality and performance indicators between groups at the post-period only.

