For every Case patient enrolled at GMC, a data analyst will run the algorithm to consume aggregate electronic health record data to find and create a database of potential participants that meet inclusion (and do not meet exclusion) criteria at control sites. A weekly occurrence of the eligibility list will occur however, depending on the rate of recruitment the study team will determine whether this needs to occur more frequently. Study team members will apply a 1:1 case-matched control strategy to identify potential control patients that match case patients in terms of sex, age category, lung cancer histology, and lung cancer clinical and/or pathological staging information. This will be done after the Case patient-participant has a Case caregiver-participant consented to ensure that Case Dyads are enrolled and available for matching. If a Case patient-participant has enrolled but the Case caregiver-participant fails to enroll, the Case patient-participant will still be eligible for the study however the study team will recruit a replacement Case Dyad with the goal of enrolling 25 Case Dyads. Case patient-participants without caregiver-participants will be removed from analyses. Similarly, if a Control patient-participant consents but a Control caregiver-participant fails to enroll, the study team will identify a replacement Control Dyad with the goal of enrolling 25 Control Dyads. Research assistants will use the database to run weekly reports to identify potential control patients at GCMC or GWV to approach for recruitment. The research assistants will verbally review the list of potential participants as well as the weekly MDC list at GCMC and GWV with clinical staff to validate that patients on the list meeting inclusion criteria and can be approached for recruitment. The research assistant will be available to speak with patients before or after their scheduled medical appointments.

For the purpose of study awareness, informational flyers will also be available to patients in the exam rooms, waiting rooms, and through Oncology Care's MDC (**Attachment X: Recruitment Flyer - Controls**).

Demographic information will be collected on all eligible participants who are asked to participate. This information will be collected as part of the Pre-Treatment Survey for Case

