#### 4.5.1 Study Flow Diagram

## 4.6 Primary Question

The primary endpoint will be difference in quality and performance metrics at the post-period associated with FCA **exposure**, evaluated between the Case Dyads and Control Dyads.

Aggregate means will be calculated for dyads and compared between groups. Sensitivity analyses may stratify these results by low-moderate-high FCA use. FCA exposure is designed to impact care coordination, patient satisfaction, patient and caregiver quality of life, perceived involvement in care, and symptom management, all quality indicators, over standard of care in control clinic sites where care coordination is less efficient, labor-intense, and often frustrating to patients and caregivers. Additionally, the Consumer Assessment of Healthcare Provider Survey, performance metrics, for Cancer Care and Health Information Technology scores for FCA users vs. controls is expected to be greater as controls would have standard of care with no additional enhancements and could utilize MyGeisinger portals.

Theoretical Domain	Parameter of interest operationalized	Perspective	Data sources or location
Quality of Care	
Patient Satisfaction with Service Quality Hospital operations and services; physicians and staff; endorsements for others
 
Family Satisfaction with Advanced Cancer Care Information giving, availability of care, physical care, psychosocial care
	Patient Caregiver	
Patient Survey Attachment A and C: Pre and Post Survey
 
Caregiver Survey Attachment B and D: Pre and Post Survey

Patient-Caregiver Outcomes	
Quality of Life Patient's functional scales, symptoms, financial impact and global health and quality of life ratings
 
Caregiver's own state, relationships, outlook, patient condition, finances, environment
 
Caregiver Burden Personal impact, other family members, medical issues, concerned about loved one
 
Clinical Outcomes Survival, remission, exacerbation, MD Anderson Symptom Inventory
	Patient Caregiver Caregiver Patient	
Patient Survey Attachment A and C: Pre and Post Survey
 
Caregiver Survey Attachment B and D: Pre and Post Survey
 
Caregiver Survey Attachment B and D: Pre and Post Survey
 
Epic EHR See section 4.8.1

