### 4.8.1 Statistical Analysis Plan

The study team will describe quality and performance indicators observed among study participants and evaluate associations between 1) difference in quality of care (satisfaction, quality of life, burden, coordinated care) associated with FCA exposure (Case Dyads vs. Control Dyads, Post-Treatment Surveys only); and 2) change in quality of care (satisfaction, quality of life, burden, coordinated care) associated with FCA use (Case Dyads Pre-Treatment Surveys vs. Post-Treatment Surveys).

Case Dyads and Control Dyads demographic and clinical information and survey responses will be fully described using frequencies and percentages for categorical variables and mean and standard deviation or median and interquartile range for continuous variables distribution dependent. To evaluate the difference in quality of care associated with FCA **exposure** (Case v. Control) will be evaluated using chi-square test, t-tests and non-parametric univariate tests distribution dependent. Mean patient and caregiver scores will be calculated for each dyad and compared between groups. Sensitivity analyses may stratify by level of FCA use (low-moderate-high) per dyad and opportunity time for FCA exposure. Case to Control patient analyses and Case to Control caregiver analyses will also be performed to detect role-level differences in perceptions of quality and performance associated with FCA exposure. To evaluate the association of the change in quality of care associated with FCA **use** difference in response between pre- and post- surveys paired t-test or ANCOVA depending on data type and distribution. Within Case Dyads, patient means will be compared with caregiver means to detect difference in quality and performance perceptions based on role.

All statistical analyses will be performed using SAS v9.4 (SAS Institute, Inc., Cary, NC, USA). All statistical tests are meant to be descriptive since this is purely an exploratory analysis.

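### Controls are matched 1:1 to Cases, but the primary comparison, as naturally read, is unpaired and unadjusted, and the analysis data list omits histology, stage and a pair identifier

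*Combined protocol and SAP*

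**What the plan says.** Section 3.3 (Specific Aim 3) sets the design: "A case-matched controlled design will be used to evaluate differences in quality and performance indicators between groups at the post-period only". Section 4.3 (Recruitment, Controls) gives the method. The team will "apply a 1:1 case-matched control strategy to identify potential control patients that match case patients in terms of sex, age category", and also on "lung cancer histology, and lung cancer clinical and/or pathological staging information". Section 4.6 makes the post-period Case v. Control difference the primary question and adds: "Aggregate means will be calculated for dyads and compared between groups".

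For that comparison, section 4.8.1 says the difference "will be evaluated using chi-square test, t-tests and non-parametric univariate tests distribution dependent". It names no pair, matching factor or covariate. The only optional stratification is by level of FCA use and opportunity time for exposure. The secondary question is treated differently, with "pre- and post- surveys paired t-test or ANCOVA depending on data type and distribution". Section 4.8.1 also states: "All statistical tests are meant to be descriptive since this is purely an exploratory analysis".

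The patient data list in 4.8.1 includes study ID, survey responses, date of birth, gender, treatment location, problem list diagnoses and encounter diagnosis codes. It has no entry for histology, stage or matched pair. Section 4.9.1 describes the study ID as linking data sources and the patient, caregiver and provider records; it describes no link from a Case to its Control.

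If a Control caregiver does not enroll, "the study team will identify a replacement Control Dyad with the goal of enrolling 25 Control Dyads". No section says how the analysis treats an inexact match or a partner lost after enrollment.

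**The concern.** The plan restricts recruitment in order to match, and then appears not to use the matching. If sex, age category, histology and stage predict the survey scores, matched dyads have positively correlated outcomes. An unpaired standard error ignores that correlation and is too large, so the precision that matching could buy is lost. Where matches are inexact, chance imbalance in the same factors stays in the unadjusted estimate.

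Inexact matches are likely on the plan's own counts. Section 4.2.1 expects 69 + 11 = 80 eligible Control patients. At the 37% consent rate given for GMC (assumed here to hold at the control sites), 80 × 0.37 = 29.6 would consent, from whom 25 dyads matched on four factors must come.

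The stake is the precision of the primary comparison, not a decision rule. Precision still counts, because sections 4.1 and 4.7 say future studies may be designed from these findings.

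**Working it through.** **Group size.** Section 4.2.1 can be reproduced: 153 × 0.5 = 76.5 (77); 77 × 0.37 = 28.5 (given as 28); 28 × 0.90 = 25.2 (25). Section 4.8.2 says 50 per group, but the design sections say 25, which is used here. The 25 already allows for 90% completion, but the last sentence of 4.2.1 can be read as a further 90%. Both readings are shown. On the second, 25 × 0.9 = 22.5 dyads per arm and, with independent losses, 25 × 0.81 ≈ 20 intact pairs remain.

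**Assumptions.** The documents give no SD, correlation, variance explained or mismatch rate. Scores are scaled to SD 1; tests are two-sided 5%; within-pair correlation is rho; R² is the share of variance explained by the four factors.

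**Step 1: unpaired test on matched pairs, 25 pairs.**
- Unpaired 95% half-width: t(.975, 48) × √(2/25) = 2.011 × 0.283 = 0.569 SD.
- Paired half-width: t(.975, 24) × √(2(1 − rho)/25) = 0.584, 0.554, 0.522 and 0.488 SD at rho 0, 0.1, 0.2 and 0.3.
- Pairing is 2.6% wider at rho = 0 and breaks even at rho = 1 − (2.011/2.064)² = 0.05.
- Simulated rejection rate of the nominal 5% unpaired test: about 3.9, 2.9 and 2.0% at rho 0.1, 0.2 and 0.3.

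**Step 2: ANCOVA on the four factors.** The simulation used four balanced binary factors with equal effects and no pair correlation beyond them. Mean 95% half-widths in SD:

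| Setting | R² 0 | 10% | 20% | 30% |
|---|---|---|---|---|
| 25 per arm, unadjusted | 0.57 | 0.57 | 0.57 | 0.57 |
| 25 per arm, ANCOVA, exact matching | 0.567 | 0.537 | 0.507 | 0.474 |
| 25 per arm, ANCOVA, 20% mismatch per factor | 0.577 | 0.547 | 0.517 | 0.483 |
| 25 per arm, ANCOVA, no effective matching | 0.593 | 0.562 | 0.531 | 0.495 |
| 90% completion, unadjusted | 0.60 | 0.60 | 0.60 | 0.60 |
| 90% completion, ANCOVA, exact matching | 0.603 | 0.573 | 0.540 | 0.504 |
| 90% completion, ANCOVA, 20% mismatch | 0.614 | 0.583 | 0.550 | 0.515 |
| 90% completion, ANCOVA, no effective matching | 0.631 | 0.599 | 0.565 | 0.528 |

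The ANCOVA rejection rate under no effect was 4.7 to 5.4% in all settings.

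**Step 3: residual imbalance.** Take a binary stage group and 20% random mismatch. The mean absolute net imbalance is 1.75 of 25. For a stage effect of 0.3 to 0.8 SD this leaves 1.75/25 × 0.3 = 0.021 to 1.75/25 × 0.8 = 0.056 SD in the unadjusted estimate. At 10% mismatch the range is 0.014 to 0.038 SD; with no matching it is 0.034 to 0.090 SD.

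**The case against.** The test families named in 4.8.1 include paired versions, so the unpaired reading is an inference. It is the natural one, because the same paragraph names a paired test only for the pre-post question, but it remains an inference.

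The criticised analysis is also valid. The matching is on exposure; with complete pairs, ignoring them leaves the mean difference in continuous scores unchanged, and the test errs on the safe side. With descriptive tests and no power target, what remains is lost precision.

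The size of that loss is undocumented. Nothing in the plan says the four factors predict satisfaction, burden, coordination or quality of life. The primary unit is the dyad mean, half of which is a caregiver score, and matching uses patient factors only; the gain may be diluted. The rejection rates in Step 1 also assume a given rho. In the model of Step 2, 20% mismatch makes rho = 0.6 × R², so R² of 10, 20 and 30% gives rho of 0.06, 0.12 and 0.18 and rejection rates of about 4.4, 3.7 and 3.1%. The 2.0% figure needs exact matching with R² of 30%, or R² of 50% with 20% mismatch.

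The data-list gap is partly clerical: date of birth and gender are listed, and histology and stage are already obtained for matching. The imbalance figures assume random mismatch, which convenience sampling does not guarantee.

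These points stand and limit the size of the concern. They do not supply a statement of how the primary analysis uses the matching.

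**Conclusion.** The concern holds, as a minor one. The plan matches 1:1, makes the matched comparison primary, and then names no paired or adjusted method for it. Histology, stage and the pair identifier are missing from the list of analysis data, and there is no rule for inexact matches or broken pairs.

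The harm is an interval that is too wide. At 25 per arm with 20% mismatch, adjustment narrows it by 3.5% if the factors explain 10% of variance (0.567 to 0.547 SD). With exact matching and 30% explained, the gain is about 16% (0.566 to 0.474 SD). If the factors explain nothing, there is no gain. Chance imbalance of 0.02 to 0.06 SD is small beside a half-width of 0.57 SD. All these sizes rest on assumed values. Confidence is medium because the unpaired reading is inferred.

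**What to change.** In section 4.8.1:

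- Make the main Case v. Control analysis of continuous scores (dyad, patient and caregiver) a linear model with group and the patient's sex, age category, histology and stage, coarsely coded. Keep dyads whose matched partner is missing.
- Where a score is markedly skewed, report the planned non-parametric test beside it. For binary outcomes, use the analogous adjusted model with few covariates.
- Give a matched-pair analysis, such as a paired t-test, as sensitivity, since ANCOVA ignores any pair correlation beyond the four factors.
- Add histology, stage and matched-pair ID to the patient data list.
- State that results stay descriptive and that adjustment does not remove the site confounding conceded in section 4.1.

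The cost is a few lines and three fields, two of them already obtained for matching. Binary coding uses four degrees of freedom. If the factors explain nothing, the interval at 25 per arm is 0.2% wider (exact matching), 2% wider (20% mismatch) or 5% wider (no effective matching); at 90% completion, 1, 3 and 5%. Break-even is at about 0.4, 4 and 9% of variance explained, or 1.5, 5 and 10% at 90% completion. With eight covariate degrees of freedom and exact matching at 25 per arm, the half-width is t(.975, 40) × √(2/25) = 0.572 SD, 0.5% wider, with break-even at 1%. Finer coding under mismatch and the adjusted binary model were not costed; both argue for few, coarse categories.

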## 4.5 Procedures

### Case Dyads:

The research assistant will approach all eligible patients in the clinic (**Attachment U: RA talking points**) to inform them of the FCA study opportunity. Patients will learn about the need to identify a caregiver who can participate in using FCA with them to enroll in the study, however patients can participate in the study regardless of caregiver participation. Also, as part of agreeing to participate the patient will need to have or establish a MyGeisinger account and the caregiver will need to have or establish proxy access to the patients' medical record (some caregivers may already have this access). Interested dyads (patient and caregiver) that agree to participate will provide consent (**Attachment F: Informed Consent - Controls**) and this will be electronically stored in REDCap by the Research Assistant, who will also facilitate access or registration to MyGeisinger for the patient and caregiver. Participants who do not receive a copy of their consent form at the time of consent will be mailed a copy of their consent form for their records (**Attachment BB: Consent Form Letter**).

Prior to enrollment in the Family Caregiver Application, the dyad will be asked to complete a Pre-Treatment Survey (**Attachment A: Pre-Treatment Survey Patient and Attachment B: Pre-Treatment Survey Caregiver**). The terms "Study Questionnaires" and "Surveys" are used interchangeably throughout this protocol and represent the same items. Patients and caregivers will receive unique Surveys. Electronic versions of the consent and survey will be available via REDCap (paper versions available upon request). Patients and caregivers can complete the consent and survey in the clinic at the baseline time point using a secure study device (i.e., study iPad with a secure link populated through REDCap) or in hard copy. When a survey is completed and returned to the study team, the patient and caregiver will each receive a \$25 gift card. The gift card will be mailed to each participant (**Attachment T: Compensation Letter**).

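### For quality of life, the planned dyad mean is most naturally read as averaging two different instruments, with no stated scale, direction or weighting

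*Combined protocol and SAP*

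**What the plan says.** Section 4.6 (Primary Question) describes the main summary as follows: "Aggregate means will be calculated for dyads and compared between groups". Section 4.8.1 (Statistical Analysis Plan) puts it this way: "Mean patient and caregiver scores will be calculated for each dyad and compared between groups". It lists satisfaction, quality of life, burden and coordinated care as the outcomes compared. It adds that separate Case-Control analyses of patients and of caregivers are also to be done. Within Case Dyads, patient means are to be compared with caregiver means to look for differences by role.

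The Section 4.6 table describes quality of life differently for the two roles:

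- Patient (source 16): "Patient's functional scales, symptoms, financial impact and global health and quality of life ratings"
- Caregiver (source 17): "Caregiver's own state, relationships, outlook, patient condition, finances, environment"

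Caregiver burden, "Personal impact, other family members, medical issues, concerned about loved one", is collected from caregivers only. Clinical outcomes, "Survival, remission, exacerbation, MD Anderson Symptom Inventory", come from the electronic record and concern the patient only. Section 4.8.1 also describes every test as descriptive and the analysis as exploratory.

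**The concern.** An average of two scores is interpretable when both are on the same scale and point the same way. The plan appears to average, for quality of life, a patient score and a caregiver score that differ in content and source, and it says nothing on how they are made comparable. It also does not say which of the several patient components listed would enter the mean.

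Two uses are affected. In the Case-Control comparison, a difference on the pooled value could not be read on either instrument. In the within-Case comparison of roles, a gap between patient and caregiver means could reflect only how the two instruments are scored. Section 4.7 expects later studies to build on these findings, and an effect without a unit serves that poorly.

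**Working it through.** **Step 1: one value or two per dyad?** The Section 4.8.1 sentence alone allows either. Two points favour one pooled value: Section 4.6 speaks of aggregate means for dyads, and Section 4.8.1 presents the role-level analyses as additional, which would be redundant if the dyad calculation already gave separate role scores. One point goes the other way: burden is on the same outcome list but has no patient score, so pooling cannot be meant for every listed outcome. Pooling is therefore the natural reading, but an inference.

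**Step 2: which outcomes does it touch?**

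| Outcome (Section 4.6 table) | Patient source | Caregiver source | Consequence |
|---|---|---|---|
| Quality of life | 16 | 17 | Different content and source: affected |
| Satisfaction | 13-15 | 13-15 | Measure names and domains differ but citations are shared: query only |
| Burden | none | 18 | Nothing to pool |
| Coordination of care | 19 | 19 | Possibly the same instrument: confirm |
| Clinical outcomes | electronic record | none | Not affected |

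**Step 3: size.** The plan has no figure to reproduce: it gives no SDs, correlations or scoring directions. The following is an illustration on assumed inputs.

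Let P and C be the patient and caregiver scores, D = (P + C)/2, with true effects dp and dc in SD units of each scale and within-dyad correlation r. Then

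effect on D in SD units = (dp·SDp + dc·SDc) / √(SDp² + SDc² + 2·r·SDp·SDc).

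Set the smaller SD to 1 and the larger to k. Assume k = 1, 2 or 4, r = 0, 0.3 or 0.5, and an effect of 0.5 SD where present. The number of dyads does not enter.

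| Scenario | Formula | k = 1 (r = 0 / 0.3 / 0.5) | k = 2 | k = 4 |
|---|---|---|---|---|
| Effect only in the smaller-spread role | 0.5/√(k²+1+2rk) | 0.354 / 0.310 / 0.289 | 0.224 / 0.201 / 0.189 | 0.121 / 0.114 / 0.109 |
| Effect only in the larger-spread role | 0.5k/√(k²+1+2rk) | as above | 0.447 / 0.402 / 0.378 | 0.485 / 0.454 / 0.436 |
| Both roles, same direction | 0.5(k+1)/√(k²+1+2rk) | 0.707 / 0.620 / 0.577 | 0.671 / 0.602 / 0.567 | 0.606 / 0.568 / 0.546 |
| Both roles, opposite directions, not aligned (raw correlation -r) | 0.5(k-1)/√(k²+1-2rk) | 0 / 0 / 0 | 0.224 / 0.256 / 0.289 | 0.364 / 0.393 / 0.416 |

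The k = 1 values in the first row, 0.29 to 0.35 SD, are the dilution that any average produces when only one role benefits. Only the departure from that range, down to 0.11 or up to 0.49 SD, comes from unequal spreads. When both roles gain and the scales agree in direction, the result is 0.55 to 0.71 SD, so nothing is lost. In the last row the sign follows the larger-spread scale. At r = 0 that scale supplies k²/(k²+1) of the variance of D: 0.50, 0.80 and 0.94 for k = 1, 2 and 4.

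**Step 4: does another planned analysis cover the gap?** For Case versus Control, yes: the role-level comparisons keep each instrument on its own scale. For the within-Case contrast of patient with caregiver means, no.

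**The case against.** The strongest reply is that the plan never says outright that the two scores are pooled, and that its instruments cannot be seen. The reference list as supplied stops at 12, so sources 16 and 17 cannot be identified, and the surveys in Attachments A-D are not in the text. If both instruments shared a range and direction, their average would have a unit, and with equal spreads neither would dominate. This stands, and is why the point is conditional. It does not remove the need to say what is meant, because an analyst could follow either reading.

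Second, the role-level Case-Control analyses are firmly planned and all tests are descriptive. That limits the harm substantially, but leaves the within-Case contrast unrepaired and the pooled value as the summary named for the primary question.

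Third, part of any dilution belongs to averaging as such. This is correct, and the figures above separate it.

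Some stronger readings are tempting but not supported:

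- **A false Case-Control difference.** A reader might infer that pooling creates one. It does not do so by itself, because the same composite is formed in both groups.
- **Proof from the survey wording.** Section 4.5 says "Patients and caregivers will receive unique Surveys". That does not show that the quality-of-life instruments differ, since coordination of care appears in both roles' surveys under one source. The evidence is the differing content and source numbers.
- **The whole primary comparison fails.** The documents show the problem only for quality of life. For satisfaction, the patient domains, "Hospital operations and services; physicians and staff; endorsements for others", differ from the caregiver domains, but the shared citations leave the matter open.

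**Conclusion.** The point holds for quality of life, on the natural reading of Sections 4.6 and 4.8.1. Unless sources 16 and 17 happen to share range and direction, the dyad mean has no clear unit and an unstated weighting set by the relative spreads. The within-Case role contrast confounds role with instrument.

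The loss is of interpretability and possibly sensitivity. Its size cannot be derived from the documents. Under the assumptions shown, a one-role effect of 0.5 SD appears as 0.11 to 0.49 SD, against 0.29 to 0.35 SD with equal spreads. With equal gains in both roles, full cancellation needs opposite directions, equal spreads and no alignment, none of which is documented. Severity is minor to should-fix, with medium confidence because the reading is inferred and the instruments are unseen.

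**What to change.** 1. State in Sections 4.6 and 4.8.1 whether the dyad calculation gives one pooled value or two role scores, and which measures it covers.
2. Make the planned patient-level and caregiver-level Case-Control comparisons the main analyses for quality of life, and for satisfaction unless its two instruments are confirmed identical. Analyse burden in caregivers only.
3. Limit the dyad mean and the within-Case role contrast to measures confirmed, against Attachments A-D, to use the same items and scoring in both roles. Coordination of care (source 19) is the main candidate. The adoption row (source 20) is not one: its stated perspective is the health system's, and adoption is not on the Section 4.8.1 list of quality outcomes.

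The cost is wording in two sections and one check of the surveys, with no new data or participants. The downside is that quality of life loses a single dyad-level summary.

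Two neighbouring matters need settling separately. The planned number of dyads per group is 25 in Section 4.2.1 but 50 in Section 4.8.2. Section 4.3 removes Case patients without a caregiver from analysis but does not say so for Controls, which affects who enters the patient-level comparison.

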#### **4.2.1 Approximate Number of Subjects**

Approximately 135 Geisinger subjects (65 patients and 50 caregivers) will participate in the study. Patients are able to participate independent of having a caregiver; therefore the number of Geisinger patients enrolled is reflective of this possibility. Our goal is to include 100 participants in our analysis (50 patients and 50 caregivers) organized as 25 Cases Dyads and 25 Control Dyads. We will enroll 20 Geisinger providers in the treatment site who will participate in this study. If a caregiver receives care at Geisinger, his/her patient-related records are not of interest to or related to this study.

Background Logic Regarding Sample Size: The number of eligible lung cancer patients was estimated from a twelve-month report (May 2016-April 2017) ("Estimate Time Period") from each respective hospital which informed the Exploratory Evaluation Study design. Patients were included if, during the Estimate Time Period, they had an active lung cancer diagnosis on the EHR problem list and had an encounter at one of the following oncology departments (Hematology Oncology Danville, Radiation Oncology Danville, Hematology Oncology GWV, Radiation Oncology GWV) ("Inclusion Criteria"). There were 153 eligible patients from GMC ("GMC Lung Cancer Patients"), 137 eligible patients from GWV ("GWV Lung Cancer Patients"), and 21 eligible patients from GCMC ("GCMC Lung Cancer Patients") for potential inclusion in the Exploratory Evaluation Study and Phase III FCA expansion rollout. Given that the Exploratory Evaluation Study period is 6 months, the estimated count of eligible patients is reduced by 50% to 77 Case patients at GMC, 69 Control patients at GWV and 11 Control patients at GCMC.

Based upon Phase II enrollment at GMC, it is anticipated that 37% of eligible GMC Lung Cancer Patients (i.e., 28) will consent to participate in the evaluation and enroll as a Dyad. Based on Phase II enrollment at GMC, 100% of these patients will identify a caregiver who consents to

*Version 1.10 – 5.24.2018*

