participate as part of a dyad. Based on Phase II observations, 90% of these Dyads (i.e., 25) will complete an intensive 8-week treatment cycle. Recognizing variability in the incidence of disease, we chose the more conservative sample size of 25 patients enrolling in the study as part of a dyad for each arm thus resulting in 25 Case Dyads and 25 Control Dyads or 100 patient-caregiver participants. Based on Phase II observations, 90% are estimated to complete the 8-week treatment cycle and study.

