#### **4.8.2 Statistical Power and Sample Size Considerations**

Power nor sample size was estimated for this exploratory evaluation study. Therefore, a sample size of 50 Case Dyads and 50 Control Dyads was selected to describe any differences in quality and performance metrics associated with FCA use. Any statistical tests are meant to be descriptive only.

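### Separate patient and caregiver Case-Control tests do not show whether the FCA association differs by role; the plan names no direct contrast, although the data for one would exist

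*Combined protocol and SAP*

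**What the plan says.** Section 4.8.1 (Statistical Analysis Plan) first compares dyad mean scores between Case and Control Dyads. It then adds two analyses by role.

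- Between arms, within role: "Case to Control patient analyses and Case to Control caregiver analyses will also be performed to detect role-level differences". The sentence goes on to connect these differences to FCA exposure. The methods named for the exposure comparison are "chi-square test, t-tests and non-parametric univariate tests distribution dependent".
- Between roles, within the Case arm: "Within Case Dyads, patient means will be compared with caregiver means to detect difference in quality and performance perceptions based on role". This follows the sentence on pre-post change with FCA use and does not itself mention FCA.

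No group-by-role term, and no between-arm comparison of the within-dyad difference, appears in the plan. Section 4.8.1 calls all tests descriptive and sets no significance level; Section 4.8.2 says that power was not estimated. Section 4.5 (Control Dyads) has both the control patient and the control caregiver complete a post-period survey.

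**The concern.** The question of whether FCA relates differently to patients' and caregivers' ratings is a question about one quantity: the Case-Control difference in patients minus the Case-Control difference in caregivers. Neither role analysis estimates it. Two separate tests can fall on opposite sides of a significance threshold by chance when the true association is identical, and with arms this small that is not rare. A report that caregivers showed a significant difference and patients did not would then be read as FCA helping caregivers only. Section 4.7 expects later studies to be designed from these findings, so such a reading could carry forward.

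The Case-only comparison does not fill the gap. Patients and caregivers may rate care differently whether or not they have FCA, and the Control Dyads that would show this are left out of it.

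**Working it through.** **Sample size in the plan.** Section 4.2.1 can be reproduced: 153 × 0.5 = 76.5, rounded to 77 eligible; 77 × 0.37 = 28.5, given as 28 enrolling; 28 × 0.90 = 25.2, given as 25. The analysis goal is "organized as 25 Cases Dyads and 25 Control Dyads". The same section then says "90% are estimated to complete the 8-week treatment cycle and study"; applied to 25 enrolled this gives 25 × 0.90 = 22.5, so 22 per arm was also run. Section 4.8.2 instead says "a sample size of 50 Case Dyads and 50 Control Dyads was selected", which conflicts and was run as a sensitivity case.

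**Assumptions, not in the documents.** Two-sided 0.05; normal scores with SD 1; the same true shift d in both roles, so no role difference exists; within-dyad correlation ρ from 0 to 0.7; arms treated as independent, as the named tests do.

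**Step 1, power of each role's test.** Two-sample t-test, noncentrality d√(n/2), 2n − 2 degrees of freedom. For n = 25 and d = 0.5: 0.5 × √12.5 = 1.77 on 48 df, power p = 0.41.

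**Step 2, exactly one role significant.** At ρ = 0 this is 2p(1 − p) = 2 × 0.41 × 0.59 = 0.48. For ρ > 0 it was simulated with bivariate normal dyads (at least 20,000 trials per setting).

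| Dyads per arm | d (SD) | ρ = 0 | ρ = 0.3 | ρ = 0.5 | ρ = 0.7 |
|---|---|---|---|---|---|
| 25 | 0 | 9% | 9% | 8% | 7% |
| 25 | 0.3 | 29% | 25% | 21% | 17% |
| 25 | 0.5 | 48% | 40% | 33% | 25% |
| 25 | 0.8 | 33% | 27% | 23% | 18% |
| 25 | 1.0 | 12% | 11% | 10% | 8% |
| 22 | 0.5 | 47% | 38% | 32% | 24% |
| 50 | 0.4 | 50% | 40% | 33% | 26% |
| 50 | 0.5 | 42% | 35% | 29% | 22% |
| 50 | 0.8 | 4% | 4% | 4% | 3% |

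**Step 3, the Case-only comparison.** Suppose the roles differ in level by 0.5 SD in both arms, so FCA plays no part. A paired t-test on 25 Case Dyads has noncentrality 0.5 × √25 / √(2(1 − ρ)): 1.77, 2.11 and 2.50 for ρ = 0, 0.3 and 0.5. It is significant about 40%, 53% and 67% of the time. With no level gap it is significant 5% of the time. The table in Step 2 does not apply to this comparison.

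**Step 4, the direct contrast.** Take patient minus caregiver within each dyad and compare arms with a two-sample t-test. With no role difference it rejects about 5% of the time at every d, ρ and n tried. The difference has SD √(2(1 − ρ)), so the standard error is √(2(1 − ρ)) × √(2/25):

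| ρ | Standard error (SD) | 95% CI half-width (× 2.01) | Power for a 0.5 SD role difference |
|---|---|---|---|
| 0 | 0.40 | 0.80 | 23% |
| 0.3 | 0.33 | 0.67 | 31% |
| 0.5 | 0.28 | 0.57 | 41% |
| 0.7 | 0.22 | 0.44 | 61% |

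**The case against.** Four points weigh on the other side.

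- The term role-level can mean Case-Control differences estimated at the level of each role, as opposed to the dyad mean. On that reading separate analyses are the right tool. The wording is ambiguous, so the criticism holds only for the other reading.
- The Case-only sentence gives its purpose as perceptions by role. Describing how patients and caregivers in Case Dyads differ is legitimate and needs no controls. The objection applies only if the result is tied to FCA, which its place after the FCA-use analysis makes easy to do.
- All tests are labelled descriptive, no threshold is set, and no rule compares p-values across roles. Section 4.1 also admits bias and limits attribution to FCA. This lowers the stakes, but a descriptive plan should still describe the quantity it says it is looking for.
- The direct contrast needs the same items in both roles. Section 4.6 gives coordination of care one source number (19) for both, but the reference list ends at 12, and one shared set of numbers (13-15) covers two differently named satisfaction measures. Section 4.5 says each role gets its own survey. A shared number therefore does not prove a shared instrument.

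A reader might infer that the two role analyses would together signal a false role difference a third to a half of the time. The documents do not support that. They state no significance level, effect size, SD or within-dyad correlation, and the rate falls well below a third over much of the plausible range. It also describes only the pair of separate tests, not the Case-only comparison.

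**Conclusion.** The point holds in conditional form. If the aim is to learn whether the FCA association differs by role, the planned analyses do not estimate it. That conclusion rests on no numerical assumption.

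The size of the risk does rest on assumptions. It arises only if significance is compared across the two separate tests, and the 33% to 48% range belongs to a common effect of 0.5 SD, 25 dyads per arm and correlation no higher than 0.5. Over correlations 0 to 0.7 the range is 17% to 29% at 0.3 SD, 8% to 12% at 1.0 SD and 7% to 9% with no effect. The figures change at the 50 dyads per arm of Section 4.8.2, which must be reconciled with Section 4.2.1. This is a worthwhile, inexpensive improvement to an exploratory plan; the separate analyses remain valid as within-role estimates.

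**What to change.** In Section 4.8.1:

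1. State what role-level differences means. Keep the separate patient and caregiver analyses as within-role Case-Control estimates with confidence intervals.
2. Check which measures use the same items in both roles; survey coordination of care is the likely candidate. For those, add the Case-Control difference in the within-dyad patient-minus-caregiver post-survey score. With complete pairs, a model with group, role, group by role and a dyad random intercept gives the same estimate. Report it with a 95% confidence interval.
3. Show the patient-caregiver gap in Control Dyads beside the gap in Case Dyads.
4. State that one role's test being significant and the other's not will not be taken as evidence that FCA works differently by role.

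The cost is SAP wording and one extra model; both arms already supply the surveys. The limit is precision: at 25 dyads per arm the interval would be about ±0.57 to ±0.80 SD for correlation 0.5 down to 0, so the interval should be reported in preference to a p-value. Satisfaction, quality of life and caregiver burden, which are measured differently by role or in one role only, would not be covered.
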